10.6 Evaluation of Toxicity

All participants will be evaluable for toxicity from the time of their first treatment with sEphB4-HSA.

10.7 Evaluation of Response

All participants included in the study must be assessed for response to treatment, even if there are major protocol treatment deviations or if they are ineligible. Each participant will be assigned one of the following categories: 1) complete response, 2) partial response, 3) stable disease, 4) progressive disease, 5) early death from malignant disease, 6) early death from toxicity, 7) early death because of other cause, or 9) unknown (not assessable, insufficient data).

All of the participants who met the eligibility criteria (with the possible exception of those who received no study medication) will be included in the main analysis of the response rate. Participants in response categories 4-9 will be considered to have a treatment failure (disease progression). Thus, an incorrect treatment schedule or drug administration does not result in exclusion from the analysis of the response rate.

All conclusions will be based on all eligible participants. Sub-analyses may then be performed on the basis of a subset of participants, excluding those for whom major protocol deviations have been identified (e.g., early death due to other reasons, early discontinuation of treatment, major protocol violations, etc.). However, these sub-analyses will not serve as the basis for drawing conclusions concerning treatment efficacy, and the reasons for excluding participants from the analysis will be clearly reported. The confidence intervals will also be provided.

11.0 ROLE OF DATA MANAGEMENT

11.1 CRF Instructions

Access to the internet data entry system for this study, Advantage eClinical, and instructions for recording of study data on CRFs will be provided by the AMC ODMC at www.AIDSCancer.org. Participating institutions are responsible for submitting data and/or data forms via Advantage eClinical in accordance with the AMC Data Entry Guide and specific form instructions, within the timelines specified by the AMC's Standards of Procedure for Site Performance Measures.

11.2 Data Quality

It is the responsibility of the AMC ODMC to assure the quality of data for the study (See [Appendix XIII](#), AMC Data and Safety Monitoring Plan). This role extends from protocol development to generation of the final study database.

11.3 Data Monitoring

This study will be monitored in compliance with AMC policies and by the CDUS Version 3.0. Cumulative protocol- and participant-specific CDUS data will be submitted electronically to CTEP on a quarterly basis. Reports are due January 31, April 30, July 31, and October 31. Instructions for submitting data using the CDUS can be found on the CTEP Web site

(<http://ctep.cancer.gov/reporting/cdus.html>).

The AMC ODMC is responsible for compiling and submitting CDUS data to CTEP for all participants and for providing the data to the Principal Investigator for review.

12.0 ETHICAL AND REGULATORY CONSIDERATIONS

12.1 IRB Approval and Informed Consent

The principles of Institutional Review Board (IRB) approval and informed consent described in the Food and Drug Administration (FDA) regulations (21 CFR Part 50 and 56) and Department of Health and Human Services (DHHS) regulations for the Protection of Human Subjects regulations (45 CFR Part 46) must be followed. IRB approval of the protocol and the informed consent form must be given in writing.

The sponsor's designee (AMC ODMC) must receive a copy of the letter of approval from the IRB, which specifically approves the protocol and informed consent, before participant enrollment. The IRB must also approve any significant changes to the protocol and documentation of this approval must be sent to the AMC ODMC. The IRB must review the research project at least once every 365 days during the duration of the project. Continuing approval of the project must also be given in writing and provided to the AMC ODMC.

Records of all study review and approval documents must be kept on file by the Investigator and are participant to inspection during or after completion of the study. AEs must be reported to the IRB according to local procedures. The IRB should receive notification of completion of the study and final report within 3 months of study completion and termination. The Investigator will maintain an accurate and complete record of all submissions made to the IRB, including a list of all reports and documents submitted.

Written informed consent will be obtained from the participant. The nature, significance, and risks associated with the study must be explained to the participant. The informed consent will describe the purpose of the study, the procedures to be followed, the risks and benefits of participation, all risks of the investigational agent(s) and/or study participation as listed in the model informed consent form, and all other elements of informed consent as required by regulation. A copy of the consent form will be given to the participant to keep.

In addition, any institution(s) conducting research according to the guidelines of this protocol is required to adhere to local and national laws and regulations governing the confidentiality and disclosure of health information.

12.2 Changes to the Protocol

Any change or addition to this protocol requires a written protocol amendment that must be approved by CTEP and the Investigator before implementation. All amendments require approval by the IRB/IEC of the treating institution. A copy of the written approval of the IRB/IEC must be sent to the ODMC.

12.3 Women and Minorities

This study is being conducted by the NCI-sponsored AIDS Malignancy Consortium (AMC). As part of their contractual obligations, each participating site within the AMC and the AMC as a whole is required to assure that the participation of women and minority participants reflects the percentage representation of these populations in their geographic region and, for the AMC, the United States as a whole. As such, it is expected that the

representation of participants on this trial will reflect the constitution of the respective populations.

Table 12-A: Accrual targets

Ethnic Category	Sex/Gender				
	Females		Males		Total
Hispanic or Latino	2	+	11	=	13
Not Hispanic or Latino	1	+	6	=	7
Ethnic Category: Total of all participants	3	+	17	=	20
Racial Category					
American Indian or Alaskan Native	0	+	0	=	0
Asian	0	+	1	=	1
Black or African-American	3	+	8	=	11
Native Hawaiian or other Pacific Islander	0	+	1	=	1
White	1	+	6	=	7
Racial Category: Total of all participants	4	+	16	=	20

(A1 = A2) (B1 = B2) (C1 = C2)

12.4 Investigator and Research Associate Registration with CTEP

Food and Drug Administration (FDA) regulations and National Cancer Institute (NCI) policy require all individuals contributing to NCI-sponsored trials to register and to renew their registration annually. This trial is sponsored by VasGene and supported by NCI and will comply with the NCI requirement for CTEP registration accordingly, while using AMC applications and processes for site registration and data entry. To register, all individuals must obtain a Cancer Therapy Evaluation Program (CTEP) Identity and Access Management (IAM) account at <https://ctepcore.nci.nih.gov/iam>. In addition, persons with a registration type of Investigator (IVR), Non-Physician Investigator (NPIVR), or Associate Plus (AP) (*i.e.*, clinical site staff requiring write access to the electronic data entry system for this protocol or acting as a primary site contact) must complete their annual registration using CTEP's web-based Registration and Credential Repository (RCR) at <https://ctepcore.nci.nih.gov/rcr>.

RCR utilizes five-person registration types.

- IVR: MD, DO, or international equivalent,
- NPIVR: advanced practice providers (*e.g.*, NP or PA) or graduate level researchers (*e.g.*, PhD),
- AP: clinical site staff (*e.g.*, RN or CRA) with data entry access to CTSU and/or AMC applications (*e.g.*, Roster Update Management System [RUMS], OPEN, Rave; Advantage eClinical for this protocol),
- Associate (A): other clinical site staff involved in the conduct of NCI-sponsored trials, and
- Associate Basic (AB): individuals (*e.g.*, pharmaceutical company employees) with limited access to NCI-supported systems.

Table 12-B: CTEP investigator registration documentation requirements

Documentation Required	IVR	NPIVR	AP	A
FDA Form 1572	✓	✓		
Financial Disclosure Form	✓	✓	✓	
NCI Biosketch (education, training, employment, license, and certification)	✓	✓	✓	
HSP/GCP training	✓	✓	✓	
Agent Shipment Form (if applicable)	✓			
CV (optional)	✓	✓	✓	

An active CTEP-IAM user account and appropriate RCR registration is required to access all CTEP and Cancer Trials Support Unit (CTSU) websites and applications. In addition, IVRs and NPIVRs must list all clinical practice sites and IRBs covering their practice sites on the FDA Form 1572 in RCR to allow the following:

- Added to a site roster
- Act as the site-protocol PI on the IRB approval
- Assigned the Clinical Investigator (CI) role on the Delegation of Tasks Log (DTL; the AMC DTL template will be used for this study; see [Section 12.5](#)).

Additional information can be found on the CTEP website at <https://ctep.cancer.gov/investigatorResources/default.htm>. For questions, please contact the RCR **Help Desk** by email at [contact].

12.5 Protocol Registration and Delegation of Tasks Log

Each site must complete a protocol-specific registration packet, including an AMC DTL using the provided AMC template or local equivalent. The Clinical Investigator (CI) is required to review and sign the DTL prior to the site receiving an approved site registration status and enrolling participants to the study. The AMC DTL template is provided in the protocol registration packet for this protocol, located on the AMC Operations web site at www.AIDSCancer.org. Any individual at the enrolling site on a participating roster may initiate the site DTL. Instructions on completing the DTL are embedded in the AMC DTL template.

The AMC DTL must be updated contemporaneously as personnel are added or removed and/or study roles and delegated tasks change. Changes must be approved by the CI, and documented by his/her initials and date, before they are implemented.

APPENDIX I: SCHEDULE OF EVALUATIONS

Baseline evaluations are to be conducted within 21 days prior to start of protocol therapy, unless otherwise specified. Scans and x-rays must be done ≤ 28 days prior to the start of therapy. In the event that the participant's condition is deteriorating, laboratory evaluations should be repeated within 48 hours prior to initiation of the next cycle of therapy. Please note, hypertension is a known and expected side effect of this drug. Please see [Section 5.4](#) for special considerations for participants with cardiac risk factors (history of hyperlipidemia, smoking, diabetes, treatment for hypertension, African American ethnicity) and specific instructions for participants who develop \geq grade 2 hypertension while on treatment.

	Eligibility	Screening/ Baseline	Cycle 1 Day 1	Cycle 1 Day 15	Cycles 2 – 12				Treatment Discont.	Post Treatment Eval.	Follow Up Visits
					Day 1		Day 15				
Informed Consent	X ^a										
Documentation of HIV status		X ^a									
KS Biopsy (Diagnostic)	X ^a										
Complete Medical History		X									
Complete Physical Exam ^s , Complete Review of Signs and Symptoms, and Review of AIDS- defining events		X	X ^g	X ^h	X ^h		X ^h		X	X	X
ECOG or KPS Performance Status	X	X	X ^g	X ^h	X ^h				X	X	
Toxicity Assessment		X ^{bb} (hyper- tension only)	X ^{bb} (hyper- tension only)	X ^{h, bb}	X ^{h, bb}				X	X	
EKG		X ^v									
KS Tumor Assessment, Photographic Record		X ^d	X ^g		X ^{h,r}				X	X ^r	X ^x
Concomitant Medication Review		X	X ^g	X ^h	X ^h						
Assess Adherence to Antiretroviral Therapy	X ^u	X	X ^g	X ^h	X ^h				X		
Review of current and prior anti- HIV therapy (if HIV positive), prior immune based therapy and prior anti-tumor therapy		X	X ^g		X ^h				X		
FAHI+KS Quality of life questionnaire (see Appendix XII)		X ^k	X ^k				X ^m (Cycle 4 only)			X	
KS staging		X ^b							X	X	
CBC with Differential, Serum Chemistries ^l		X	X ^h	X ^h	X ^h		X ^h		X	X	
CD4 and CD8 Count (T Cell Subsets), and HIV-1 plasma		X ^b	X ^l		X ^h (Cycle 4, 7,				X		

	Eligibility	Screening/ Baseline	Cycle 1 Day 1	Cycle 1 Day 15	Cycles 2 – 12				Treatment Discont.	Post Treatment Eval.	Follow Up Visits
					Day 1		Day 15				
RNA, if HIV-positive					10 only)						
HHV-8 Viral Loads (see Appendix III)		X ^{k, y}	X ^{k, y} (predose)		X ^{aa} (Cycle 4, 7, 10 only)				X		
Serum or Urine HCG Pregnancy Test ^c		X ^c	X ^q								
Education and counseling guidance		X ^g									
Dispense sEphB4-HSA			X	X	X		X				
Urinalysis		X	X ^w		X ^w				X		
Peripheral blood sEphB4-HSA levels (see Appendix II)			X (predose and immediately prior to end of infusion)	X (predose)	X ⁿ (predose)		X ⁿ (predose)				
Peripheral blood (for immune studies) (see Appendix III)		X ^{k, z}	X ^{k, z} (predose)	X	X ^o (predose)						
Peripheral blood (for PBMCs for Research) (see Appendix III)		X ^{k, y}	X ^{k, y} (predose)	X	X ^{aa} (Cycle 4, 7, 10 only)				X		
5-mm KS Biopsy (formalin-fixed), and 5-mm KS Biopsy (RNA later)		X ^k	X ^k (predose)	X ⁱ (after Day 15 dose)							
Chest X-ray ^f , CT Scan ^p		X ^b									
ACSR Donation (Screening or Day 1, optional with consent)		X ^j									

^a To be done any time prior to study enrollment

^b To be done ≤ 28 days prior to study enrollment

^c To be done ≤ 14 days prior to study enrollment

^d To be done ≤ 7 days prior to study enrollment

^e Pregnancy test to be done on females of childbearing potential

^f Participants with a positive CXR or minimal symptoms suggestive of pulmonary involvement of KS will have a CT thorax performed. CXR not required if a thoracic CT has been performed

^g Baseline assessments can be done on Day 1, or < 14 days prior to first dose of study drug

^h Labs may be done up to 7 days prior to days 1 and 15 of each cycle; interval history and physical exam must be done up to 7 days prior to study agent administration.

ⁱ To be done after Cycle 1, Day 15 dosing. Can be done any time after treatment on Cycle 1, Day 15 and before treatment of Cycle 2, Day 1

^j To be done at any time from time of study enrollment to Day 1, if the participant consents

^k To be completed within 14 days prior to Cycle 1, Day 1 of study drug. Baseline and Day 1 can be the same day

- ¹ Baseline and Day 1 can be the same (as long as done within 4 weeks of treatment)
- ^m To be administered anytime between Cycle 4, Day 15 and Cycle 5, Day 15
- ⁿ After Cycle 1, pre-dose blood for sEphB4-HSA trough levels only to be drawn days 1, 15 of Cycle 2.
- ^o Only on Day 1 of Cycles 2, 4, and 6; to be done before study treatment dosing. Given this will be a fresh blood sent at room temperature overnight, if the blood for immune studies cannot be collected on Monday-Wednesday (i.e., the dose is administered on Thursday or Friday), this blood work can be obtained the Monday AFTER the dose was given.
- ^p Only needed if symptomatic or specific findings on CXR
- ^q To be done within 24 hours of first dose of study drug
- ^r Photographs to be obtained when the KS response category changes
- ^s Includes vital signs (temperature, pulse, BP, respiratory rate), height (baseline only), weight. For cycles 2-12, only vital signs and weight are to be collected on Day 15.
- ^t Includes liver enzymes (AST (SGOT), ALT (SGPT), alkaline phosphatase), BUN, creatinine, electrolytes (sodium, potassium, chloride, CO₂, calcium, phosphorus, glucose), total protein, albumin, bilirubin (direct and indirect)
- ^u Participant must be on a stable antiretroviral regimen for at least 12 weeks prior to study entry.
- ^v QTcF (Fridericia Correction Formula) > 480 on 2 out of 3 EKG's (if first EKG is < 480, no need to repeat; if first EKG is > 480, repeat twice for a total of 3 EKG's)
- ^w Negative, Trace, or 1+ protein: continue with sEphB4-HSA; ≥ 2+, see [Section 5.3](#) for dosing changes
- ^x No photographs needed.
- ^y Must be obtained on Sunday-Thursday.
- ^z Must be obtained on Monday-Wednesday.
- ^{aa} If scheduled day is Fri-Sat, please obtain sample 7 days before or after scheduled day to be mailed express overnight on a Sunday-Thursday.
- ^{bb} Hypertension is an expected adverse event within the class of anti-neoplastic drugs affecting the vascular endothelial growth factor (VEGF) pathway. In participants with a baseline blood pressure (BP) ≥ 120/80 mm Hg and cardiac risk factors (history of hyperlipidemia, smoking, diabetes, treatment for hypertension, African-American ethnicity),⁶⁷ hypertension should be anticipated and therefore may need more aggressive management *prior to* first dose of study drug. In these cases, it is recommended that an internal medicine specialist or cardiologist be consulted to assist in management of hypertension. See [Section 5.4](#) for specific instructions for titration of antihypertensive drugs for those with cardiac risk factors, as well as specific instructions for participants who develop ≥ grade 2 hypertension while on treatment. See [Section 8.2.1.3](#) for BP measurement instructions.

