2.3.8 Dosing in clinical trial

A phase I trial in refractory/relapsed solid tumors has been completed. The following dose levels were tested in the phase I trial: 2.5 mg/kg, 5 mg/kg, 10 mg/kg and 15 mg/kg administered weekly on Days 1, 8, 15, and 22; and 10 mg/kg, 15 mg/kg and 20 mg/kg administered every 14 days (2 weeks) on Days 1 and 15, by I.V. infusion for 60 minutes. The weekly dosing schema and schedule was chosen based on safety of weekly dosing in animal studies of doses up to 30 mg/kg. No DLTs were seen in this weekly dosing, however dose accumulation was noted. Cohorts consisting of 10 mg/kg, 15 mg/kg and 20 mg/kg, with administration every 14 days (2 weeks), were added to the phase I trial, given the dose accumulation noted with weekly dosing. The phase I maximum tolerated dose (MTD) has been reached with 2 of 6 participants, at 20 mg/kg administered every 14 days,

experiencing grade III hypertension that was not responsive to therapy, requiring dose reduction to 15 mg/kg every two weeks, and long half-life of 7 - 10 days. Therefore, the dose of 15 mg/kg every 2 weeks, administered on Days 1 and 15, was initially used as the starting dose in this Phase II trial.³¹

Based on updated data (unpublished communication with VasGene, 8/2018) from other trials with sEphB4-HSA (ClinicalTrials.gov ID NCT03146871), which take into consideration rates of hypertension and drug accumulation, other trials have been modified to use a dose of sEphB4-HSA of 10 mg/kg every 2 weeks. Based on this information combined with initial experience in this study, this trial is amended with protocol version 4.0 to use a dose of 10 mg/kg every 2 weeks, administered on Days 1 and 15 of each cycle. In addition, other unpublished studies (ClinicalTrials.gov ID NCT02717156 and NCT03049618), which dosed sEphB4-HSA at 10 mg/kg weekly, showed grade 3/4 hypertension in 3/21 and 3/19 participants, respectively. Given the updated information of drug accumulation in the context of an approximately 5-day half-life of sEphB4-HSA, the weekly dose will not be used in this trial.

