- 8.2.2.10 Biologic endpoints: peripheral blood for biologic endpoints described in [Appendices I](#) and [III](#) will be collected at Day 1 of Cycles 2, 4, 6, 7, and 10. The samples include blood for immune studies on Day 1 of Cycles 2, 4, and 6 to be done before study treatment dosing. Given this will be a fresh blood sent at room temperature overnight, if the blood for immune studies cannot be collected on Monday-Wednesday (i.e., the dose is administered on Thursday or Friday), this blood work can be obtained the Monday AFTER the dose was given. Blood for HHV-8 viral loads and archived research purposes on Day 1 of Cycles 4, 7, and 10, and at treatment discontinuation.
- 8.2.2.11 Biologic endpoints: peripheral blood for pharmacokinetics as described in [Appendices I](#) and [II](#) will be collected on Day 1 and 15 of Cycle 2; the samples will be drawn pre-dose.
- 8.2.2.12 If HIV positive, T-lymphocyte subsets (CD4 and CD8) to be done every three cycles (Day 1 of Cycle 4, 7, and 10), and at treatment discontinuation.
- 8.2.2.13 If HIV positive, HIV-1 plasma RNA to be done every three cycles (Day 1 of Cycles 4, 7, and 10), and at treatment discontinuation).
- 8.2.2.14 FAHI+KS quality of life questionnaire on Day 15 of Cycle 4 (questionnaire may be performed up until Day 15 of Cycle 5). Those who have HIV-negative KS will not have the HIV portion scored. See [Appendix XII](#) for KAH1+KA questionnaire.

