- Affix the FED-EX airbill on blank side of the shipper making sure that it is marked “FED-EX PRIORITY OVERNIGHT.”
- Mark “OTHER” in the air bill under “Packaging.” Please use the FedEx # available on the AMC member’s only website.
- Under air bill section “Special Handling” indicate “YES-SHIPPERS DECLARATION NOT REQUIRED.”
- Place “From/To” information onto areas provided on the shipper.

BLOOD SPECIMENS should be shipped by overnight express at room temperature to:

AMC Network Resources Laboratory
[name]
George Washington University Medical Center
[name]
[name]

- Make certain that shipper is already either pre-labeled with “UN#3373” stamp or make a paper label with “UN#3373” and affix it to the shipper.
- Make certain that the net volume of the specimen being shipped is written in the space provided on the shipper or make a separate label with the volume in mL and affix to the shipper.
- Affix airbill to shipper so that the “UN” and “VOLUME” labels are visible.
- RETAIN THE TOP COPY OF THE AIRWAY BILL FOR YOUR RECORDS.
- Place the box in the FedEx pickup area at your site or call to request a package pickup.

Please Note: The shippers will be mailed back to each AMC site.

Specimens should be sent by 24-hour shipment at room temperature. If collecting on a Friday through Saturday where 24-hour shipment is not possible, please see Section below for instructions.

INSTRUCTIONS FOR PERIPHERAL BLOOD SPECIMENS (FRIDAY – SATURDAY)

Specimens for future research and HHV-8 (i.e., fresh whole blood) must be mailed overnight to the AMC Biorepository to arrive Monday-Friday. Therefore, participants who are scheduled for the study drug on a Friday or Saturday (thereby making the blood for future research and HHV-8 viral loads scheduled for Friday or Saturday), alternative timing of blood draws will have to be made.

To accommodate this issue, peripheral blood for future research and HHV-8 can be drawn and overnight shipped **up to 7 days before or after the scheduled date; samples must be drawn on a Sunday through Thursday.**

SEE PART B: SPECIMEN PREPARATION, PACKAGING, AND SHIPMENT FOR FULL DETAILS OF SHIPPING

Correlative studies shall be sent to:

The AMC biorepository will send the specimens to centers performing each correlative study as stated below:

- *Samples for HHV-8 viral load* will be shipped to the AMC Genomics Core labs at the University of North Carolina, Chapel Hill.

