- Samples need to be shipped OVERNIGHT EXPRESS at ambient temperature to George Washington University Medical Center. Samples should be sent Monday - Wednesday. Please notify George Washington University Medical Center (see contact below) one week prior to anticipated collection of samples to ensure proper handling. For samples that are collected Thursday through Sunday, please notify George Washington University Medical Center two weeks in advance so that arrangements can be made for alternative collection dates. Of note, it has been written into the protocol that if a drug is being administered on Thursday through Sunday (and therefore pre-dose samples will be obtained on a Thursday or Friday), the blood samples for immune studies may be obtained and shipped the Monday AFTER treatment has been administered.
- Please use the FedEx # available on the AMC member's only website to ship specimens.
- Shipments can be sent to:

George Washington University Medical Center
[name]
[name]
[name]

Email: [contact] **RECORD OF SPECIMENS**

Each sample must be labeled. Unlabeled samples will be discarded. Each sample should be labeled using a Sharpie pen with the following information:

Protocol #: AMC-096
11-digit AMC participant #
Study cycle #/Day#
Date and time of collection
Specimen Type: Whole Blood
Specimen Purpose:

This study will track specimens via GlobalTraceSM, a component of the AMC Advantage eClinical system. The GlobalTraceSM shipment manifest must accompany all specimen shipments.

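### Immune blood specified as pre-dose at Cycles 2, 4 and 6 may be drawn on the Monday after a late-week infusion, well above trough exposure, and Section 10.4 has no rule for such samples

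*Combined protocol and SAP*

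**What the plan says.** Section 2.5.2.3, Section 8.2.2.10, Appendix I and Appendix III all place the on-treatment immune blood before dosing. Section 8.2.2.10 puts it this way: "The samples include blood for immune studies on Day 1 of Cycles 2, 4, and 6 to be done before study treatment dosing". Appendix I, footnote o, agrees: "Only on Day 1 of Cycles 2, 4, and 6; to be done before study treatment dosing".

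Both Section 8.2.2.10 and footnote o then make an exception, because the blood travels fresh overnight. If it cannot be collected Monday to Wednesday, "this blood work can be obtained the Monday AFTER the dose was given". Their example of when this applies is that "the dose is administered on Thursday or Friday".

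Appendix IX carries the same exception: "the blood samples for immune studies may be obtained and shipped the Monday AFTER treatment has been administered". Its trigger is wider: "if a drug is being administered on Thursday through Sunday". Section 2.5.2.3 states no exception, and Appendix III only refers the reader to Appendix IX for samples falling Thursday to Sunday.

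The baseline immune sample is protected: Appendix I requires it pre-dose and, by footnote z, on a Monday to Wednesday. Section 4.1 asks for Cycle 1 Day 1 on a Monday where possible. Section 10.4 plans descriptive statistics and, depending on enrolment, a Wilcoxon rank sum test of clinical response against changes in markers that include immune cell counts and activation. It does not mention samples drawn after dosing or time since dose.

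**The concern.** Objective 1.2.3.3 asks what the drug does to immune response, and the parent objective asks how that relates to clinical response. The stated design compares each participant's drug-free baseline with samples at the end of a dosing interval. Under the exception, some participants would instead be sampled 3 or 4 days after an infusion. If peripheral immune markers move with drug level, the two kinds of sample do not measure the same thing.

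The difference tends to stay with the participant. Days 1 and 15 of a 28-day cycle fall on the same weekday, so someone dosed on Thursdays or Fridays would tend to meet the exception at all three visits unless a delay resets the schedule. The mixing is therefore mainly between participants, in at most 20 people. Drug levels do not resolve it: they are drawn pre-dose and stop at Cycle 2 Day 15, so none describes exposure at a late Monday draw.

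**Working it through.** The plan gives no figure on this point, so there is none to reproduce.

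**Inputs.**
- Dosing interval: 14 days (Section 4.1).
- Half-life: Section 2.3.8 gives two statements, 7 to 10 days from the phase I trial and, later, "in the context of an approximately 5-day half-life of sEphB4-HSA". They differ, so 5, 7 and 10 days are all shown.
- Days from dose to the following Monday, d: Thursday 4, Friday 3, Sunday 1.
- Assumption: one-compartment exponential decay at steady state.

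**Exposure at the permitted late draw, relative to the intended trough:** ratio = 2^((14 − d) / half-life).

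| Half-life | Thursday dose | Friday dose | Sunday dose (Appendix IX only) |
|---|---|---|---|
| 5 days | 2^(10/5) = 4.0 | 2^(11/5) = 4.6 | 2^(13/5) = 6.1 |
| 7 days | 2^(10/7) = 2.7 | 2^(11/7) = 3.0 | 2^(13/7) = 3.6 |
| 10 days | 2^(10/10) = 2.0 | 2^(11/10) = 2.1 | 2^(13/10) = 2.5 |

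Cycle 2 Day 1 is only the third dose. Summing the doses given so far, the ratios there are slightly higher: 4.07 and 4.68 (5 days) and 2.21 and 2.37 (10 days) for Thursday and Friday.

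**Exposure if the draw is moved earlier instead.** For a draw e days before the dose, ratio = 2^(e / half-life). The nearest permitted day is Wednesday.

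| Half-life | Thursday dose (e = 1) | Friday dose (e = 2) | Sunday dose (e = 4) |
|---|---|---|---|
| 5 days | 1.15 | 1.32 | 1.74 |
| 7 days | 1.10 | 1.22 | 1.49 |
| 10 days | 1.07 | 1.15 | 1.32 |

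**Effect on the Section 10.4 comparison.** The documents do not link concentration to any immune marker, so this part is illustrative. It used 6,000 simulated trials with 9 responders, 11 non-responders and a two-sided rank sum test at 0.05. The late-draw shares and the size of the post-dose shift are assumed.

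| Late draws, responders / non-responders | Post-dose shift | True difference | Rejection rate |
|---|---|---|---|
| none | none | 0 | 4.7% |
| 40% / 40% | 1 SD | 0 | 4.5% |
| none | none | 1.3 SD | 74% |
| 40% / 40% | 1 SD | 1.3 SD | 65% |
| 40% / 40% | 2 SD | 1.3 SD | 44% |
| 40% / 10% | 1 SD | 0 | 8% |
| 60% / 10% | 1 SD | 0 | 15% |
| 60% / 10% | 2 SD | 0 | 34% |

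With equal shares the false-positive rate holds and power falls. It rises only when late draws are more common in one response group. The mean change from baseline moves by (share of late draws) × (shift), for example 0.4 × 1 SD = 0.4 SD, whether or not the shares are equal.

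**The case against.** The strongest case for leaving this alone is that the exception is a permission of unknown use. Section 4.1 prefers Monday starts precisely because of sample timing, and a participant who stays on Mondays never meets it. Section 2.5 calls the correlative studies exploratory, Section 2.5.2.3 makes the immune work conditional on funding, and the rank sum test is itself conditional on numbers. The immune sample label records the date and time of collection, so time since dose could be worked out afterwards. The primary endpoint is untouched. All of this stands and limits how much weight the point can bear.

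It does not remove the point. Monday is a preference, and Section 5.6 lets a Tuesday or Wednesday dose slip by up to 48 hours into Thursday or Friday, while longer delays reset the cycle. A recorded draw time helps only if the analysis uses it, and Section 10.4 does not say that it will.

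Three stronger readings might be inferred and are not supported:

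- **That dosing weekday confounds the relation with response.** This needs weekday to be associated with response, for instance through site. Nothing in the documents shows that, and the inflated error rates above come only from assumed imbalance.
- **That the whole pharmacodynamic series mixes trough and post-dose samples.** The rule covers peripheral immune blood only. On-treatment biopsies are deliberately taken after the Cycle 1 Day 15 dose, and the immune sample on that day carries no pre-dose label in Appendices I and III.
- **That HHV-8 and archived blood have the same defect.** Those Friday or Saturday draws may move "up to 7 days before or after the scheduled date" (Appendix VIII), but on treatment they have no stated pre-dose requirement to breach.

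The Sunday column also deserves caution. It rests on one sentence of Appendix IX, whose own parenthesis speaks of samples falling on a Thursday or Friday.

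**Conclusion.** The inconsistency is real and narrow. Three places allow a sample defined as pre-dose to be taken after the dose, and their weekday triggers disagree. For Thursday or Friday dosing the permitted draw sees about 2.0 to 4.6 times the intended trough, given one-compartment decay, a 14-day interval and half-lives of 5 to 10 days. If immune markers respond to drug level, the consequences are added noise and a shifted mean change from baseline. Bias in the comparison by response is conditional and not shown. How many participants are affected cannot be read from the documents. For an exploratory endpoint with pending funding, this warrants a text correction and a short analysis rule.

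**What to change.** In Section 8.2.2.10, Appendix I footnote o and Appendix IX, replace the Monday-after rule with a draw on the nearest Monday to Wednesday before the dose, and state one weekday trigger in all three. In Section 10.4, derive time since last dose from the recorded collection date and time and the infusion date. Flag any immune sample drawn post-dose, and report the pre-dose series with and without those samples. Leave the HHV-8 and archived-blood window as it is.

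The cost is small. The exception already requires a draw on a day other than the dosing day. Footnote h already allows routine laboratory work up to 7 days before Days 1 and 15, so the immune tube can share that visit.

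There are two downsides. The early draw is not a true trough: it is about 1.07 to 1.32 times trough on the Wednesday before a Thursday or Friday dose, and more for a weekend dose. The analysis without late samples also has fewer observations in an already small trial, which is why both versions should be shown.
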